|--|---|

| | |
|--|---|
| | 
skin cancers, or localized, low-grade tumors deemed cured and not treated with systemic therapy
 
14. History of allergy to study drug components.
 
15. Prisoners or subjects who are involuntarily incarcerated
 
16. Subjects who are compulsorily detained for treatment of either a psychiatric or physical (eg. infectious disease) illness
 
17. Inability to comply with restrictions and prohibited activities/treatments.
 |
| Test Treatment(s) (Description) | |
| | Cabozantinib will be initiated at full dose (60 mg every day) which will be modified upon development of adverse events according to the manufacturer's recommendations. Treatment will continue until symptomatic tumor progression, unacceptable adverse events, patient decision or death. |
| | Safety reporting |
| 
All AEs that occur after the patient has signed informed consent until at least 30 days after the last dose of the study treatment must be recorded in the CRF.
 
The documentation should be confirmed with a note in the patient's file. An abnormal laboratory result considered clinically significant—e.g. any which causes the patient's withdrawal from the study, requires treatment or causes obvious clinical manifestations, or which is assessed as relevant by the investigator—must be reported as an AE. Each event should be described in detail, together with the start and end dates, severity, relationship to the investigational medicinal product, measures taken and outcome.
 
All actions taken concerning the study treatment to resolve the AE (drug withdrawal, drug suspension, dose reduction, unchanged dose, dose escalation, not applicable, not known) will be documented.
 
Notice to the IECs of all relevant events (e.g. SAEs, Suspected Unexpected Serious Adverse Reactions [SUSARs]) will be given by the sponsor and/or investigator in accordance with the applicable regulations.
 
The processing and communication of all relevant events (SAEs, SUSARs) to the authorities will be carried out by the sponsor in accordance with current legislation.
 
The sponsor will inform all sites of relevant adverse events (e.g. SUSARs) in accordance with current legislation.
 | |
| Standard of Reference/Standard of Truth* | |

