4.1 TREATMENT PLAN

4.1.1 SCREENING PHASE

Study entry is defined as the date that the Informed Consent has been signed by the patient. No patient may undergo any screening procedures that are not considered standard of care to assess his/her eligibility to receive protocol treatment, or commence protocol treatment, prior to signing the informed consent form. The time period between study entry and the commencement of protocol treatment is not to exceed 28 days. Patients may only commence protocol treatment after all eligibility criteria have been confirmed. After signing the informed consent and upon documentation of eligibility, the patient will be allocated with an enrolment number and registered in an enrolment log. The patient identification number will be multi-digit, to represent the investigational site and an enrolment number that will be unique to each subject. All patients referred for possible participation in this study must be assessed at screening to confirm the patient's eligibility. All documentation supports the inclusion and exclusion criteria and screening investigation results are to be retained by the Investigator and made available for monitoring by the study

Sponsor including source data verification. All patients assessed as ineligible to be enrolled in the study after study entry are considered screening failures. The investigator will have their initials recorded on the Patient Screening Log and no further data will be collected for these patients. The Patient Screening Log will include the reason(s) for the patient not meeting the eligibility criteria and will be maintained by the site and copies retained by the study Sponsor. Patient who withdrew consent after study entry but before treatment for any reason will be considered screening failures and should be registered in the screening log.

The study monitor should be contacted in the event of any query or uncertainty relating to a patient's eligibility to receive protocol treatment:

[name]

BCLC group, Liver Unit, Hospital Clinic de Barcelona
Email: [contact]
[contact];
[contact]

[name]

BCLC group, Liver Unit, Hospital Clinic de Barcelona
Email: [contact]
[contact];
[contact]

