- Sexually active fertile subjects and their partners must agree to use medically accepted methods of contraception (eg, barrier methods, including male condom, female condom, or diaphragm with spermicidal gel) during the course of the study and for 4 months after the last dose of study treatment
- Female subjects of childbearing potential must not be pregnant at screening. Females of childbearing potential are defined as premenopausal females capable of becoming pregnant (ie, females who have had any evidence of menses in the past 12 months, with the exception of those who had prior hysterectomy). However, women who have been amenorrheic for 12 or more months are still considered to be of childbearing potential if the amenorrhea is possibly due to prior chemotherapy, antiestrogens, ovarian suppression, low body weight, or other reasons.
- Subjects must consent to perform a tumor liver biopsy within 4 weeks before starting cabozantinib, allowing the acquisition of a tumor sample for performance of correlative studies. A

formalin-fixed, paraffin embedded (FFPE) tumor tissue block of tumor sample should be stored at local sites for correlative studies, as described in [Section 7.4](#). For these biopsies, subjects must have a soft tissue tumor lesion that can be biopsied at acceptable clinical risk, as judged by the investigator. Subjects must consent to the pre-treatment fresh liver biopsy as a condition of protocol participation. If adequate tissue is not obtained during the first procedure then a repeat biopsy should be considered based on the investigator's assessment of clinical risk. However, **biopsies at the time of radiological tumor progression are not required to meet eligibility.** Tumor biopsy is recommended at the time of tumor progression development. However, patients who develop radiologic tumor progression, should have performance status 0/1 and preserved liver function. Finally, patients with symptomatic tumor progression will not be biopsied.

All patients on cabozantinib treatment must stop cabozantinib 5-7 days before performing the biopsy to avoid the risk of bleeding. They will be visited 5-7 days after the biopsy to re-start cabozantinib.

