7.2 SAFETY ASSESSMENTS

7.2.1 ASSESSMENTS AND DOCUMENTATION OF ADVERSE EVENTS

All AEs occurring after the subject has signed the informed consent form (IC) up until the end of the safety follow-up period (30 ± 7 days after permanently discontinuing cabozantinib administration) must be fully recorded in the subject's CRF.

Adverse event documentation is event-based (using the NCI-CTCAE version 5.0 guidelines). Adverse events should be collected past 30 days after the study treatment stop for all AEs that were ongoing at the end of treatment as well as new adverse events that in the opinion of the investigator could be related to study treatment. (Information may be obtained via phone call).

Documentation must be supported by an entry in the subject's file.

Adverse events should be followed until resolution or stabilization unless, in the investigator's opinion, the condition is unlikely to resolve due to the patient's underlying disease.

If any patient dies within 30 days of last dose of study drug, the investigator will inform the sponsor and record the cause of death in detail within 24 hours on a SAE form.

A laboratory test abnormality considered clinically relevant, e.g. causing the subject to withdraw from the study, requiring treatment or causing apparent clinical manifestations, or judged relevant by the investigator, should be reported as an AE. Each event should be described in detail along with start and stop dates, severity, relationship to investigational product, action taken and outcome.

Note that all the patients will receive the "alert card" reporting useful information in case of need such as the name of the clinical trial, the name and contacts of PI or collaborators.

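### Section 4.1.1 ends data collection for screening failures while Section 7.2.1 requires adverse events from consent to be recorded and followed, and the mandatory liver biopsy falls in between.

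*Protocol*

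**What the plan says.** **Screening (Protocol Section 4.1.1).** "Study entry is defined as the date that the Informed Consent has been signed by the patient". "All patients assessed as ineligible to be enrolled in the study after study entry are considered screening failures". Their initials go on the Patient Screening Log with the reason for failure, and "no further data will be collected for these patients". The same section adds: "Patient who withdrew consent after study entry but before treatment for any reason will be considered screening failures". An enrolment number is issued only after eligibility has been documented.

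**Adverse events.** Section 7.2.1 covers "All AEs occurring after the subject has signed the informed consent form (IC) up until the end of the safety follow-up period", which it sets at 30 ± 7 days after cabozantinib is permanently stopped. These events must be fully recorded in the CRF. They must be followed until they resolve or stabilise, unless the investigator thinks resolution unlikely because of the underlying disease. The Synopsis, under Safety reporting, has the same starting point and also makes CRF entry compulsory; its sentence opens "All AEs that occur after the patient has signed informed consent until at least 30 days after the last dose of the study treatment must".

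**Biopsy.** Section 5.1.2 states: "Subjects must consent to the pre-treatment fresh liver biopsy as a condition of protocol participation". The tissue is for correlative studies, the biopsy is due within 4 weeks before the first dose, and a repeat is to be considered if tissue is inadequate. Table 5 places it at screening. Sections 2 and 7.4 say the samples will be analysed in a second study, and only if this trial meets its safety end-point.

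**Analysis.** The SAP Safety Set (Section 8.1) needs at least one dose of cabozantinib. The adverse-event summaries (Section 8.6.5.3.7) cover treatment-emergent events. Table 43 and Listing 30 cover screen failures, with no content specified.

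**The concern.** The period between consent and first dose is not free of study risk. It contains an invasive procedure that the trial requires for research. In a patient who has that procedure and is then found ineligible, a site that obeys Section 4.1.1 stops collecting data, while a site that obeys Section 7.2.1 goes on recording and following events. Neither section refers to the other, and nothing says which prevails, so sites may act differently.

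At stake is the completeness of the harms record for a study-mandated procedure: complications that appear or worsen after the screen-failure date, and the outcome of those already present. Section 10.2 makes the DSMB responsible for the ongoing safety of study patients, and it can weigh the biopsy's risk only if these events are captured and passed to it.

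**Working it through.** The trial reports no figure on this point, so the check sets the sections side by side.

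1. **Does the biopsy follow consent?** Yes. Section 4.1.1 says "No patient may undergo any screening procedures that are not considered standard of care" before signing consent. A fresh biopsy taken for correlative studies as a condition of participation is a study procedure, so it comes after consent. Sections 5.1.2 and 7.1 place it before the first dose.

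2. **Can a biopsied patient still become a screening failure?** Yes. The biopsy may be up to 4 weeks (28 days) before the first dose. The haematology, renal, bilirubin, albumin, transaminase and QTcF criteria are judged within 7 days before the first dose. The biopsy may therefore precede the deciding laboratory values by up to 28 − 7 = 21 days. The documents do not fix the order, so this is permitted but not required.

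3. **Which rule applies on each side of the ineligibility decision?**

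| Timing of event or information | Synopsis and Section 7.2.1 | Section 4.1.1 |
|---|---|---|
| Event after consent, before the decision | Record in CRF | No bar; the stop applies from the decision onwards |
| Outcome and follow-up of that event after the decision | Section 7.2.1: follow until resolved or stable | Stop |
| New event after the decision | Record in CRF | Stop |

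The conflict lies in the second and third rows.

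4. **When does recording end for a patient never dosed?** It is undefined. Section 7.2.1 counts from stopping cabozantinib and the Synopsis from the last dose. Section 7.2.3 takes the SAE observation period from Section 8.2, which says only that reports are collected over the course of the study (Section 8.2.1).

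5. **Does other text settle it?** Not clearly. Section 8.1.1 defines an adverse event in a subject who has been given a medicinal product, and Section 8.1.3 covers deaths during use of the product. Read literally, neither reaches harm before dosing. The SAE form in Section 14.8 does offer a protocol procedure as a possible cause, which suggests that such events are meant to be captured.

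6. **Does the SAP report these events?** A patient never dosed is outside the Safety Set and so outside the adverse-event tables. Table 43 and Listing 30 could carry the events, but nothing says that they will.

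7. **Is the primary analysis touched?** No. The 14-patient interim look, the total of 40 and the primary endpoint analyses all concern dosed patients.

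**The case against.** The best defence is that Section 7.2.1 has no exception for screening failures and already requires recording and follow-up. Section 7.2.3 requires SAEs to be reported within 24 hours and followed, and Section 7.2.6.1 treats examination findings after consent as adverse events. Screening results are kept for source verification, and the log keeps the reason for failure. On this view Section 4.1.1 is an administrative sentence that no site would use to ignore a complication. Part of this stands: an event before the ineligibility decision is recordable. It does not remove the conflict after that decision, and a log reason may name only the failed criterion, without grade, cause or outcome.

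A reader might infer more than the documents support.

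- **That biopsy harm is lost outright, or that only mild complications are recorded.** A complication that itself causes ineligibility comes before the decision, so it falls in the recordable period.
- **That a biopsy bleed leads directly to exclusion.** The bleeding criterion in Section 5.2.1 makes an exception for other significant bleeding with reversible external causes, and haemoglobin is judged on values within 7 days before therapy. Whether a given bleed excludes a patient is uncertain.
- **That the gap has a known size.** Suppose a fraction f of consented patients fail screening, a fraction b of those failures were biopsied, and all 40 dosed patients were biopsied. Failures are F = 40 × f/(1 − f), and the biopsied failures' share of all biopsied patients is bF/(40 + bF). With f = 0.20, F = 10; with f = 0.40, F = 26.7. If b = 1, the shares are 10/50 = 20% and 26.7/66.7 = 40%. If b = 0.5, they are 5/45 = 11% and 13.3/53.3 = 25%. If b = 0, the share is zero. The documents give neither f nor b, so none of these is an estimate.

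Patients who withdraw are a separate matter. Section 11.3 says that no further data are collected when a patient ends participation, and any remedy must respect that.

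**Conclusion.** The concern holds as a conflict between stated rules. For a consented, biopsied patient later found ineligible, Section 4.1.1 stops the data collection that the Synopsis and Section 7.2.1 require. What is cut off is later events, outcome and follow-up. Separately, the adverse-event window has no end for a patient never dosed. This is more than missing detail, because a site that follows Section 4.1.1 as written stops following harm from a study procedure.

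The effect is confined to safety oversight of the biopsy. It also covers biopsied patients who fail for reasons unrelated to the biopsy. The number affected cannot be estimated from the documents. What the DSMB would see is also unknown, because its charter is a separate document. The conclusion assumes only that some patients are biopsied before their eligibility is settled, which the windows allow.

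**What to change.** Reconcile Section 4.1.1, the Synopsis and Section 7.2.1:

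- **Section 4.1.1:** state that for any consented patient who had a study-specific procedure such as the biopsy, AEs and SAEs from consent are recorded and procedure-related events are followed even if the patient becomes a screening failure. Make this subject to any withdrawal of consent to further data collection (Section 11.3).
- **Section 7.2.1 and the Synopsis:** define when the adverse-event window ends for a patient never dosed.
- **Identifier:** give such patients a screening identifier so that an adverse-event page can be opened, since the enrolment number comes only after eligibility is documented.
- **SAP:** list these events with Table 43 and Listing 30, outside the Safety Set and the primary endpoint, and supply them to the DSMB.

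The cost is a few sentences of amendment, a small CRF/EDC change for the identifier and adverse-event page, and one extra listing. The sample size, the interim rule and the planned endpoint analyses do not change.

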4.1.2 CABOZANTINIB

The choice of dosage (starting dose of 60 mg) and schedule to be used in this trial is based on available data accumulated in previous Phase I, II and III trials and approved to treat HCC with cabozantinib.

The study drug will be administered orally. The investigator or designated study personnel is responsible for dispensing the study drug to patients.

Patients should be instructed to not eat anything for at least 2 hours before through 1 hour after taking cabozantinib. Subjects should be instructed to not make up vomited doses and to maintain the planned dosing schedule. Subjects should not make up for missed doses if more than 12 hours have elapsed after the time the subject would usually take cabozantinib. In the event of missed doses, subjects should not take 2 doses to make up for the one the subject missed.

Any unused study treatment must be returned to the study site for drug accountability and disposal.

Cabozantinib will be initiated at full dose (60 mg/day) and the dose will be modified upon development of adverse events according to the manufacturer's recommendations. Treatment will be continued until symptomatic tumor progression, unacceptable adverse events, patient decision or death. Criteria for cabozantinib dose reduction or escalation and to resume treatment are described in [Section 6.1.4.1](#)

4.1.3 END OF THE STUDY

After discontinuation from study therapy, there is 1 follow-up visit required within seven days of discontinuation (on site visit), and additional survival follow-up (on-site or phone visits). The study will end

when survival follow-up collection has concluded. The last visit will be defined as the latest follow-up Visit. Additional survival follow-up may continue beyond the time of this analysis.

4.1.4 DISCONTINUATION OF CABOZANTINIB

Subjects MUST discontinue study medication:

- Withdrawal of informed consent (subject's decision to withdraw for any reason)
- Any clinical AE, abnormal laboratory test results or any illness which, in the opinion of the investigator, indicates that continued participation in the study is not in the best interest of the subject.
- Clinical deterioration ([Section 6.1.7](#))
- Pregnancy
- Termination of the study by the promoter
- Specific criteria for discontinuation of outlined in ([Section 6.1.6](#))
- Loss of ability to freely provide consent through imprisonment or involuntary incarceration for treatment of either a psychiatric or physical (eg, infectious disease) illness.
- Protocol defined disease progression unless subject is eligible for treatment beyond progression ([Section 6.1.7.1](#)).
- In the case of pregnancy, the investigator must immediately notify the Medical Monitor/designee of this event. In most cases, the study drug will be permanently discontinued in an appropriate manner. If the investigator determines a possible favorable benefit/risk ratio that warrants continuation of study drug, a discussion between the investigator and the Principal Investigator must occur.
- All subjects who discontinue should comply with protocol specified follow-up procedures as outlined in section. The only exception to this requirement is when a subject withdraws consent for all study procedures or loses the ability to consent freely (ie, is imprisoned or involuntarily incarcerated for the treatment of either a psychiatric or physical illness). If a subject was withdrawn before completing the study, the reason for withdrawal must be entered on the appropriate CRF page.

4.1.5 POST STUDY DRUG STUDY FOLLOW-UP

In this study, overall survival is a secondary endpoint. Subjects who discontinue study drug must continue to be followed for collection of survival follow-up data until death or the conclusion of the study. Survival follow-up visits should be planned every 3 months from Follow-Up Visit-1 and may be performed by phone contact or office visit.

4.1.6 WITHDRAWAL OF CONSENT

Subjects who request to discontinue study treatment will remain in the study and must continue to be followed for protocol specified follow-up procedures. The only exception to this is when a subject

specifically withdraws consent for any further contact with him/her or persons previously authorized by subject to provide this information. Subjects should notify the Investigator of the decision to withdraw consent from future follow-up in writing, whenever possible. The Investigator should explain the withdrawal of consent in detail in the medical records, as to whether the withdrawal is from further treatment with study drug only or also from study procedures and/or post treatment study follow-up, and entered on the appropriate CRF page.

4.1.7 LOST TO FOLLOW-UP

All reasonable efforts must be made to locate subjects to determine and report their ongoing status. This includes follow-up with persons authorized by the subject as noted above. Lost to follow-up is defined by the inability to reach the subject after a minimum of three documented phone calls, faxes, or emails or whatsapp messages as well as lack of response by subject to one registered mail letter. All attempts should be documented in the subject's medical records. If it is determined that the subject has died, the site will use permissible local methods to obtain the date and cause of death. If after all attempts, the subject remains lost to follow-up, then the last known alive date as determined by the investigator should be reported and documented in the subject's medical records.

5. PATIENT POPULATION

For entry into the study, the following criteria MUST be met. Eligibility criteria for this study have been carefully considered to ensure the safety of the study subjects and to ensure that the results of the study can be used.

5.1 INCLUSION CRITERIA

5.1.1 SIGNED WRITTEN INFORMED CONSENT

Willing, able and mentally competent to provide written informed consent.

5.1.2 TARGET POPULATION

- HCC diagnosed according to criteria of American Association for the Study of Liver Diseases (AASLD) definition in 2010.
- Intolerant to sorafenib according to RESORCE trial definition or patients who received treatment different to sorafenib as first-Line treatment.
- The subject has disease that is not amenable to a curative treatment approach (eg, transplant, surgery, radiofrequency ablation)
- Recovery to \leq Grade 1 according to (CTCAE) v.5.0. from toxicities related to any prior treatments, unless the adverse events are clinically no significant and/or stable on supportive therapy
- Respect the 15 days of first-line treatment washout before starting cabozantinib
- Age \geq 18 years old on the day of consent
- ECOG performance status of 0 or 1
- Adequate hematologic function, based upon meeting the following laboratory criteria within

7 days before starting therapy:

- a. absolute neutrophil count (ANC) $\geq 1200/\text{mm}^3$ ($\geq 1.2 \times 10^9/\text{L}$)
- b. platelets $\geq 60,000/\text{mm}^3$ ($\geq 60 \times 10^9/\text{L}$)
- c. hemoglobin $\geq 8 \text{ g/dL}$ ($\geq 80 \text{ g/L}$)
- Adequate renal function, based upon meeting the following laboratory criteria within 7 days before starting therapy:
 - a. Serum creatinine $\leq 1.5 \times$ upper limit of normal or calculated creatinine clearance $\geq 40 \text{ mL/min}$ (using the Cockroft-Gault equation: $(140 - \text{age}) \times \text{weight (kg)} / (\text{serum Creatinine} \times 72 [\text{mg/dL}])$ for males. (For females multiply by 0.85).

AND

- b. urine protein/creatinine ratio (UPCR) $\leq 1 \text{ mg/mg}$ ($\leq 113.1 \text{ mg/mmol}$) or 24-hour urine protein $< 1\text{g}$
- Child-Pugh Score of A
- Total bilirubin $\leq 2 \text{ mg/dL}$ ($\leq 34.2 \mu\text{mol/L}$) within 7 days before starting therapy
- Serum albumin $\geq 2.8 \text{ g/dL}$ ($\geq 28 \text{ g/L}$) within 7 days before starting therapy
- Alanine aminotransferase (ALT) and aspartate aminotransferase (AST) ≤ 5.0 upper limit of normal (ULN) within 7 days before starting therapy
- Hemoglobin A1c (HbA1c) $\leq 8\%$ within 28 days before starting therapy (if HbA1c results are unavailable [eg, hemoglobin variant], a fasting serum glucose $\leq 160 \text{ mg/dL}$)
- Antiviral therapy per local standard of care if active hepatitis B (HBV) infection
- Capable of understanding and complying with the protocol requirements and signed informed consent
- Sexually active fertile subjects and their partners must agree to use medically accepted methods of contraception (eg, barrier methods, including male condom, female condom, or diaphragm with spermicidal gel) during the course of the study and for 4 months after the last dose of study treatment
- Female subjects of childbearing potential must not be pregnant at screening. Females of childbearing potential are defined as premenopausal females capable of becoming pregnant (ie, females who have had any evidence of menses in the past 12 months, with the exception of those who had prior hysterectomy). However, women who have been amenorrheic for 12 or more months are still considered to be of childbearing potential if the amenorrhea is possibly due to prior chemotherapy, antiestrogens, ovarian suppression, low body weight, or other reasons.
- Subjects must consent to perform a tumor liver biopsy within 4 weeks before starting cabozantinib, allowing the acquisition of a tumor sample for performance of correlative studies. A

formalin-fixed, paraffin embedded (FFPE) tumor tissue block of tumor sample should be stored at local sites for correlative studies, as described in [Section 7.4](#). For these biopsies, subjects must have a soft tissue tumor lesion that can be biopsied at acceptable clinical risk, as judged by the investigator. Subjects must consent to the pre-treatment fresh liver biopsy as a condition of protocol participation. If adequate tissue is not obtained during the first procedure then a repeat biopsy should be considered based on the investigator's assessment of clinical risk. However, **biopsies at the time of radiological tumor progression are not required to meet eligibility.** Tumor biopsy is recommended at the time of tumor progression development. However, patients who develop radiologic tumor progression, should have performance status 0/1 and preserved liver function. Finally, patients with symptomatic tumor progression will not be biopsied.

All patients on cabozantinib treatment must stop cabozantinib 5-7 days before performing the biopsy to avoid the risk of bleeding. They will be visited 5-7 days after the biopsy to re-start cabozantinib.

